The total number of patients to be enrolled overall and in each module will depend on the types and number of tumor modules added to the main study and country-specific ancillary studies. The number of patients and sites to be involved in individual countries will be dependent on each module or ancillary study.

It is anticipated that the total enrollment period for the overall study will be approximately 2 to 3 years, with an overall duration of 4 to 5 years.

Study design

Study Duration		Phase of Development
Estimated date of first patient enrolled (United States)	Q1 2017	Phase IIIb
Estimated date of final data cut-off (Global)	Q2 2020	
Estimated date of last patient follow up (Global) Q2		

Study Flow chart

Tumor specific modules detail which treatment regimen, combination therapy or monotherapy will be used. Patients will continue to receive study treatment as long as they are receiving clinical benefit in the opinion of the Investigator unless any of the criteria for treatment discontinuation are met first. Survival follow up will continue until the final data cut-off (DCO).

Study design

This is an open-label, multi-center, study to determine the short and long-term safety of fixed doses of durvalumab 1500 mg + tremelimumab 75 mg combination therapy or durvalumab 1500 mg monotherapy in patients with advanced solid malignancies.

This study is modular in design, each tumor specific Module allowing evaluation of the safety, tolerability, and antitumor activity of the combination of durvalumab + tremelimumab or durvalumab alone in different solid tumors.

The modules are developed as separate components appended to this protocol. Additional modules may be added as part of this protocol as decisions on additional tumor types and/or exploratory sub-studies are made.

One or more of these modules will be opened in a given country / region based on local patient population prevalence, and results of feasibility studies.

The protocol (and each tumor specific module) consists of a screening period, a treatment period, a 90–day safety follow up period, and a survival follow up period.

Patients will attend a safety follow up visit 90 days after study treatment discontinuation. Thereafter, patients will be contacted by phone or electronic communication every 3 months for survival status until the final data cut-off (DCO).

Investigational product, dosage and mode of administration

Durvalumab + tremelimumab combination therapy

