6.3 Recording of adverse events

6.3.1 Time period for collection of adverse events

Adverse events and SAEs will be collected from time of the patient signing the ICF until the follow up period is completed (90 days after the last study treatment administration). If an event that starts post the defined safety follow up period noted above is considered to be due to a late onset toxicity to study drug then it should be reported as an AE or SAE as applicable.

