6.3.12 Safety data to be collected following the final DCO of the study

For patients continuing to receive durvalumab treatment after final DCO and database closure, it is recommended that the patients continue the scheduled site visits and Investigators monitor the patient's safety laboratory results prior to and periodically during treatment with durvalumab in order to manage AEs in accordance with the durvalumab Dose Modification and Toxicity Management Guidelines (see Section 6.9.1). All data obtained post the final DCO and database closure will be recorded in the patient notes but, with the exception of SAEs, will not otherwise be reported for the purposes of this study.

All SAEs that occur in patients still receiving durvalumab treatment (or within the 90 days following the last dose of durvalumab treatment) post the final DCO and database closure must be reported as detailed in Section 6.4.

6.4 **Reporting of serious adverse events**

All SAEs have to be reported, whether or not considered causally related to durvalumab \pm tremelimumab, or to the study procedure(s). All SAEs will be recorded in the CRF, except SAEs occurring after the DCO and database closure. After the DCO, SAEs will be reported via paper SAE forms and recorded in AstraZeneca database.

If any SAE occurs in the course of the study, then Investigators or other site personnel inform the appropriate AstraZeneca study representatives (or designees) within one day ie, immediately but **no later than 24 hours** of when he or she becomes aware of it.

The designated AstraZeneca study representative (or designee) works with the Investigator to ensure that all the necessary information is provided to the AstraZeneca Patient Safety data entry site within 1 calendar day of initial receipt for fatal and life-threatening events and within 5 calendar days of initial receipt for all other SAEs.

For fatal or life-threatening AEs where important or relevant information is missing, active follow up is undertaken immediately. Investigators or other site personnel inform AstraZeneca study representatives of any follow up information on a previously reported SAE within one calendar day ie, immediately but **no later than 24 hours** of when he or she becomes aware of it.

The reference documents for definition of expectedness are the IBs for durvalumab and tremelimumab, as applicable to the tumor specific Module.

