4. ANALYSIS METHODS

4.1 General principles

No hypothesis testing is planned for this single arm study. Each module will be summarised separately.

The general principles as mentioned below will be followed throughout the study:

- Descriptive statistics will be used for all variables, as appropriate, and will be presented separately for each module. Descriptive safety and efficacy data from the STRONG study may be utilized as supporting evidence for health authority considerations.
- Continuous variables will be summarized by the number of observations, mean, standard
 deviation, median, minimum, and maximum. For log transformed data it is more
 appropriate to present geometric mean, coefficient of variation (CV), median, minimum
 and maximum. Categorical variables will be summarized by frequency counts and
 percentages for each category.
- Unless otherwise stated, percentages will be calculated out of the population total.
- Exact CIs for proportions will be calculated using the Clopper-Pearson method.
- For percentiles of survival times based on the Kaplan-Meier method (eg, median survival), CIs will be calculated using the default method available in the SAS LIFETEST procedure (ie, the Klein and Moeschberger extension of the Brookmeyer-Crowley method).
- For point-estimates of survival based on the Kaplan-Meier method (eg, for OS at 12 months), CIs will be calculated using the default method available in the SAS LIFETEST procedure (ie, using Greenwood's estimate of standard error and a log-log transformation).
- For continuous data the mean and median will be rounded to 1 additional decimal place compared to the original data. The standard deviation will be rounded to 2 additional decimal places compared to the original data. Minimum and maximum will be displayed with the same accuracy as the original data.
- For categorical data, percentages will be rounded to 1 decimal place.
- SAS® version 9.3 or higher will be used for all analyses.

Baseline will be the last assessment of the variable under consideration prior to the intake of the first dose of study treatment.

All data collected will be listed.

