- Death related to disease under investigation ONLY, as determined by investigator (including deaths occurring within 90 days after last dose of study medication and deaths occurring after the 90 days post dosing window)
- TEAEs with outcome of death ONLY
- AEs with outcome of death ONLY and onset date falling after 90 days follow-up period
- Deaths related to disease under investigation, as determined by the investigator, and with TEAE with outcome of death
- Deaths related to disease under investigation, as determined by the investigator, and with AE with outcome of death and onset date falling after 90 days follow-up period
- Deaths that occurred 90 days after last dose, and unrelated to AE (ie no AE with outcome of death) or disease under investigation

- Patients with unknown reason for death
- Other deaths

Summary of long term tolerability

To assess long term tolerability, provided that there are a sufficient number of patients with events to warrant it (\geq 10 events), prevalence plots and cumulative incidence plots will be presented for each AESI category and for any other events considered important after review of the safety data.

A prevalence plot provides information on the extent to which the events may be an ongoing burden to patients. The prevalence at time t after first dose of study treatment is calculated as the number of patients experiencing the event divided by the number of patients receiving study treatment or in safety follow-up at time t; generally, t is categorised by each day after dosing. The prevalence will be plotted over time. Multiple occurrences of the same event are considered for each patient but a patient is only counted in the numerator whilst they are experiencing one of the occurrences of the event. The raw cumulative incidence is the actual probability that a patient will have experienced their first occurrence of the event by a given time point.

Treatment exposure

The following summaries related to study treatment will be produced for the SS:

- Total exposure, actual exposure, and total number of cycles received will be summarised separately for the initial treatment phase and the re-treatment phase. For the modules with combination therapy, those summaries will be carried out once for each drug separately and once for combination separately from monotherapy.

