- Number of, reasons for, and duration of dose delays/interruptions of durvalumab and tremelimumab. Dose interruptions will be based on investigator initiated dosing decisions. In addition, interruptions due to AEs and due to reasons other than AEs will be summarized separately.
- Number of infusions received.
- Exposure over time will be plotted.

For patients on study treatment at the time of the OS analysis, the DCO date will be used to calculate exposure.

Subsequent Therapy

Subsequent therapies received will be summarized.

Laboratory assessments

Laboratory assessments are to be measured 90 days after last dose during the safety follow-up visit, per institutional care guidance only. Data obtained up until the 90 days following discontinuation of immunotherapy agents or until the initiation of the first subsequent therapy following discontinuation of treatment (whichever occurs first) will be used for reporting. This will more accurately depict laboratory toxicities attributable to study treatment only as a number of toxicities up to 90 days following discontinuation of immunotherapy agents are likely to be attributable to subsequent therapy.

A small selection of summaries of laboratory data may also be produced containing data from initiation of the first subsequent therapy following discontinuation of study treatment until 90 days following discontinuation of immunotherapy agents (i.e. summarising the laboratory data collected on patients taking subsequent therapy during the safety collection follow-up window post discontinuation of study treatment). These outputs will only be produced if the number of laboratory toxicities observed warrant the inclusion of such outputs for interpretational purposes. Any data post 90 days last dose will not be summarised.

Data summaries will be provided in International System (SI) of units.

For continuous laboratory assessments absolute value, change from baseline and percentage change from baseline will be summarised using descriptive statistics at each scheduled assessment time.

Shift tables for laboratory values by worst NCI CTCAE grade will be produced The laboratory parameters for which CTCAE grade shift outputs will be produced are:

- Haematology: Haemoglobin, Leukocytes, Lymphocytes (count, absolute), Neutrophils (count, absolute), Platelets.
- Clinical chemistry: ALT, AST, ALP, Total bilirubin, LDH, calcium, lipase, amylase, Sodium hypo and hyper, Potassium hypo and hyper, Creatinine, Urea nitrogen.

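### The AESI cumulative incidence plots use a raw proportion and call it the actual probability; with staggered entry and a fixed cut-off it can only match or understate that probability, mostly for late onsets

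*SAP*

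**What the plan says.** SAP section 4.2.1, under Summary of long term tolerability, plans two plots for each AESI category with at least ten events: prevalence and cumulative incidence. For the second it says only: "The raw cumulative incidence is the actual probability that a patient will have experienced their first occurrence of the event" by a given time. It gives no denominator, estimator, censoring rule or treatment of competing events. The companion prevalence plot does have a stated denominator, the "number of patients receiving study treatment or in safety follow-up at time t". The general rule in SAP section 4.1 is: "Unless otherwise stated, percentages will be calculated out of the population total".

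Four other statements bear on who is observed, and for how long:

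- The Protocol synopsis expects that the "total enrollment period for the overall study will be approximately 2 to 3 years", with first enrolment in Q1 2017 and final DCO in Q2 2020.
- Protocol section 6.3.1 collects adverse events from consent "until the follow up period is completed (90 days after the last study treatment administration").
- The SAP expects some patients to be on drug at the cut-off: "For patients on study treatment at the time of the OS analysis, the DCO date will be used to calculate exposure" (section 4.2.1, Treatment exposure).
- Protocol section 6.3.12 says of what happens afterwards: "All data obtained post the final DCO and database closure will be recorded in the patient notes but, with the exception of SAEs", are not otherwise reported for the study.

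**The concern.** A raw proportion at time t equals the probability of a first event by t only if every patient has been followed to t, or has had the event, died or completed the safety window before t. Patients who died or completed the 90-day window without an event are correctly event-free. The problem is the patient whose window is still open at DCO at some time before t: any later first onset is outside the data, but the patient still counts in the denominator.

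The share of such patients can only grow with t, so the loss falls on the late part of the curve. Protocol section 1.2 says the study should inform on rare or new immune-mediated events arising with long-term administration. A reader told that the curve is the actual probability would take its late flattening as a safety finding, when part of it may be caused by the cut-off.

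**Working it through.** **The plan's own figures.** The SAP states no value for any cumulative incidence. Its only design probability (section 1.3) is over 75% for at least ten events with N = 1200 and true incidence 1%. Exact binomial: P(X ≥ 10) = 1 − Σ(x = 0 to 9) C(1200, x) 0.01^x 0.99^(1200−x) = 0.759. This reproduces, but does not bear on the plot.

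**Direction.** For each patient let E be the time to first onset, W the end of the adverse-event window (death, or last dose plus 90 days if sooner), and C the time from first dose to DCO.

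- Quantity named in the SAP: F(t) = P(E ≤ min(t, W)).
- Raw proportion over the safety set: R(t) = #{E ≤ min(t, W, C)} / N.
- Expected value: E[R(t)] = F(t) − P(C < E ≤ min(t, W)).

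The subtracted term cannot be negative. It is zero when no patient reaches DCO before min(t, W).

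**Calendar inputs from the documents.** Accrual is 24 to 36 months. From the start of Q1 2017 to Q2 2020 is 39 months (1 April 2020) to 42 months (30 June 2020). With 36-month accrual the last patients therefore have 39 − 36 = 3 to 42 − 36 = 6 months of follow-up; with 24-month accrual and DCO at month 39 they have at least 39 − 24 = 15 months.

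**Inputs that are assumptions.** Uniform accrual; exponential time on treatment with median 3 or 6 months; exponential survival with median 9 months; a 3-month window after treatment, cut short by death; onset hazards per month before/after month 6 of 0.01/0.01, 0.02/0.005 and 0.005/0.01.

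**Simulation of R(t) against F(t)** (2,000,000 patients per scenario; range over the six combinations of treatment duration and hazard):

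| Accrual / DCO (months) | Still at risk at DCO | Relative shortfall, month 12 | Relative shortfall, month 24 | Absolute, month 24 (points) | Share of month 12-24 onsets missed |
|---|---|---|---|---|---|
| 24 / 39 | 0.2-1.4% | 0% | 0-0.9% | 0.00-0.04 | 4-7% |
| 36 / 42 | 2.5-5.9% | 0.3-2.7% | 0.4-5.9% | 0.04-0.26 | about a quarter |
| 36 / 39 | 6-11% | 2-7% | 2-11% | 0.2-0.5 | about a third |

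Two rows behind the last line, both at month 24:

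- Median treatment 6 months, hazard 0.005 then 0.01: F = 4.30%, R = 3.85%, shortfall (4.30 − 3.85)/4.30 = 10.5%.
- Median treatment 3 months, hazard 0.02 then 0.005: F = 8.55%, R = 8.37%, shortfall (8.55 − 8.37)/8.55 = 2.1%.

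**Sensitivity to time on treatment.** With a constant hazard of 0.005 per month, no separate death process and median treatment of 3, 6 or 12 months, the month-24 shortfall runs from essentially nil (3.52% against 3.53%; accrual 24, DCO 39, median 3) to (7.22 − 5.89)/7.22 = 18% (accrual 36, DCO 39, median 12).

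**Would the planned Kaplan-Meier analysis supply the missing figure?** In that same model with accrual 36, DCO 39, median treatment 6 months and N = 1200, the month-24 estimates are raw 4.5%, Aalen-Johansen 5.2%, and one minus Kaplan-Meier 10.9% when the end of the window is censored. The last is close to 1 − exp(−0.005 × 24) = 11.3%, the incidence if nobody ever left observation. It errs in the other direction.

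**The case against.** **The SAP does not say that patients at risk at DCO count as event-free.** That is correct, and a reader should not take it as SAP text. It is inferred from the word raw and the default denominator. The default yields where something else is stated, and the neighbouring prevalence plot shows that the authors could use an at-risk denominator. What remains is that the SAP names the raw quantity, gives it no other denominator and equates it with a probability. If another estimator was meant, it is not named.

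**Other outputs cover long-term tolerability.** A reader might infer that this plot stands alone. It does not: there are prevalence plots, Kaplan-Meier time to onset by AESI category with a censoring date, and event rates per 100 patient-years by preferred term. None of them gives cumulative incidence by time point. Prevalence measures current burden. The rates do not vary with time. The Kaplan-Meier output is limited to the quartiles, so an AESI whose estimated incidence stays below 25% has no quartile to report, and the method as named does not treat death as competing.

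**The size may be negligible.** This stands in part. Treatment duration, survival, hazard shape and the accrual pattern are assumptions, and the rule defining final DCO is left to the module (Protocol section 9.3), whose text was not available here. One plausible scenario gives 1% or less. Larger figures can be produced by placing DCO right after the end of accrual, but nothing in the documents says that will happen. For scale, SAP Table 1 gives a 95% interval of 3.8-6.4% for an incidence of 5% at N = 1200, wider than a shortfall of 0.2-0.5 points. That interval describes sampling error, however, and a larger trial does not remove a bias.

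**The analysis is descriptive and the primary outcome is not taken from this plot.** Both are true. A reader should not infer that the primary number and percentage with exact interval is invalidated; it is presented as an observed proportion.

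**Conclusion.** The description of the raw curve as the actual probability is wrong under this design: entry is staggered, patients on drug are expected at the cut-off, and non-serious events after DCO and database closure are not reported for the study. If the curve is the proportion of the whole safety set, as the SAP's default implies, the direction is certain: it equals or understates the probability.

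The size is not known. It depends mainly on how many patients are on treatment or within 90 days of the last dose at DCO, which the documents do not give. Over the main scenarios above, the month-24 understatement ranges from negligible to about a tenth in relative terms and is at most about half a percentage point; longer treatment would increase it. The effect on the late segment is larger, up to about a third of onsets between months 12 and 24.

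The documents do not support a claim of gross bias, or a claim about the primary endpoint. They do support changing the estimator, because the late segment is what the plot is meant to show.

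**What to change.** Replace the sentence in SAP section 4.2.1 with a definition of the plotted quantity:

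- **Estimator:** Aalen-Johansen cumulative incidence of the first treatment-emergent AESI in the category, timed from first dose.
- **Competing events:** death, or completion of the 90-day window, without an event. Ending at the window is a choice of estimand and should be stated as such. Events starting later and attributed to late toxicity remain in the separate table that the SAP already plans.
- **Censoring:** at DCO, or at earlier loss of adverse-event follow-up. Withdrawal of consent is an example, since Protocol section 3.10.2 then allows only survival follow-up.
- **Display:** numbers at risk beneath each plot.
- **Wording:** delete the claim of actual probability. If the raw curve is also kept, label it as the observed proportion and state its denominator.

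The cost is one SAP edit and a standard procedure on dates already collected. No new data are needed.

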5.3 Safety assessments

5.3.1 Laboratory safety assessments

Blood and urine samples for determination of clinical chemistry, hematology, coagulation (only if clinically indicated), and urinalysis will be taken at the times indicated in the assessment schedules and as clinically indicated (see Sections 4.1 through 4.3 and Table 2).

Clinical laboratory safety tests, including serum pregnancy tests, will be performed in a licensed clinical laboratory according to local standard procedures. Sample tubes and sample sizes may vary depending on the laboratory method used and routine practice at the site. Urine pregnancy tests may be performed at the site using a licensed test (urine or serum pregnancy test). Abnormal clinically significant laboratory results should be repeated as soon as possible (preferably within 24 to 48 hours).

Additional safety samples may be collected if clinically indicated at the discretion of the Investigator. The date, time of collection, and results (values and units) will be recorded on the appropriate CRF.

The laboratory variables to be measured are presented in Table 3.

Laboratory safety variables

Table 3

Hematology/ Hemostasis (whole blood)	White blood cell (WBC) count with differential, platelet count, red blood cell (RBC) count, hemoglobin (Hb), hematocrit, mean corpuscular volume (MCV), mean corpuscular hemoglobin concentration (MCHC)					
Clinical chemistry (serum or plasma)	Serum creatinine, total bilirubin, aspartate transaminase (AST), alanine transaminase (ALT), thyroid stimulating hormone (TSH), blood urea nitrogen (BUN), lipase, amylase, electrolytes (potassium, calcium, sodium), lactase dehydrogenase					
Urinalysis (local laboratory or dip-stic per institutional care) ^a	Hb, leukocytes, protein, glucose, bilirubin ^a , urobilinogen ^a , ketones, specific gravity					
Urine microscopy	WBC/high power field (HPF), RBC/HPF, epithelial cells, casts, crystals					
Pregnancy test for women of child-bearing potentia	Serum pregnancy tests performed for all women of childbearing potential at screening. At baseline and each treatment visit, a urine pregnancy test (dip-stick or at a local laboratory) or serum pregnancy test will be performed					
Other safety tests (screening only) ^b	Hepatitis B surface antigen, hepatitis C antibody, HIV antibodies (eg, HIV-1 and HIV-2)					

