Additional laboratory tests (where clinically indicated only)	Free tri-iodothyronine (T3) and free thyroxine (T4) ^c , creatinine clearance, alkaline phosphatase (ALP), autoimmune antibody test ^d					
(a) Tests for urine bilirubin and urobilinogen will be done (per institutional standard method) at baseline only, and repeated only as clinically indicated.						
	At screening only, for the evaluation of eligibility criteria.					
	If TSH is abnormal or there is clinical suspicion of an AE related to the endocrine system					
	then free T3 and free T4 testing will be done.					
thyroiditis,	If a patient experiences an AE that is thought to be possibly of autoimmune nature (eg thyroiditis, pancreatitis, hypophysitis, or diabetes insipidus), the Investigator should collect a blood sample for appropriate autoimmune antibody testing by a local laboratory.					

The hematology and clinical chemistry should be performed at a local laboratory at or near to the Investigator site. Urinalysis should be performed at a local laboratory (at or near to the Investigator site) or by dip-stick per institutional care. Tests for urine bilirubin and urobilinogen will be done (per institutional standard method) at baseline only, and repeated only as clinically indicated.

Sample tubes and sample sizes may vary depending on laboratory method used and routine practice at the site. Clinically significant (as assessed by the Investigator) laboratory abnormalities will be recorded in the CRF as AEs. Laboratory results relevant to / associated with AESIs will be recorded in the CRF.

Additional safety samples may be collected during the study if clinically indicated at the discretion of the Investigator and according to standard medical practice. The Investigator should make an assessment of the available results with regard to clinically relevant abnormalities. The laboratory results should be signed and dated, and retained at center as source data for laboratory variables. For information on how AEs based on laboratory tests

Note: In case a patient shows an AST or ALT \geq 3 ULN or total bilirubin \geq 2 ULN please refer to APPENDIX D for further instructions (also see Section 6.3.8).

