3.1.2.3 Laboratory data

Laboratory data will be collected throughout the study, from screening to the follow-up visits as described in the CSP. Blood and urine samples for determination of haematology, clinical chemistry, and urinalysis will be collected as described in section 5.3.1 of the CSP. For the definition of baseline and the derivation of post baseline visit values considering visit window and how to handle multiple records, derivation rules as described in section 3.1.3 below will be used.

Change from baseline in haematology and clinical chemistry variables will be calculated for each post-dose visit on treatment. CTC grades will be defined at each visit according to the CTC grade criteria using local or project ranges as required, after conversion of lab result to corresponding preferred units. The following parameters have CTC grades defined for both high and low values: Potassium, Sodium, and Glucose so high and low CTC grades will be calculated.

Absolute values will be compared to the project reference range and classified as low (below range), normal (within range or on limits of range) and high (above range). The maximum or minimum on-treatment value (depending on the direction of an adverse effect) will be defined for each laboratory parameter as the maximum (or minimum) post-dose value at any time.

Local reference ranges will be used for the primary interpretation of laboratory data at the local laboratory. Project (AZ standard) reference ranges will be used throughout for reporting purposes. The denominator used in laboratory summaries of CTC grades will only include evaluable patients, in other words those who had sufficient data to have the possibility of an abnormality.

For example:

- If a CTCAE criterion involves a change from baseline, evaluable patients would have both a pre-dose and at least 1 post-dose value recorded.
- If a CTCAE criterion does not consider changes from baseline, to be evaluable the patient need only have 1 post dose-value recorded.

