For TSH absolute value and change from baseline will be summarised using descriptive statistics at each scheduled assessment time. Shift tables showing the change from baseline to maximum and from baseline to minimum will also be produced. Free T3 and free T4 will be listed only as they are to be tested only if clinically indicated.

ECGs

ECG data will not be summarized nor listed as only high/low values are reported in eCRF

Vital signs

Vital signs will summarised by study visit. Box plot of absolute values will be produced.

Physical examination

Individual physical examination data will not be listed. Physical examination abnormalities will be reported as AEs and included in AE listings.

ECOG performance status

Shift in Eastern Cooperative Oncology Group (ECOG) performance status (see appendix F of the CSP) will be summarised.

Other Safety Data

Data from positive pregnancy tests will be listed only. Safety findings reported in the CRF to support the monitoring and evaluation of imAEs will be listed.

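### ALP is tested only on clinical indication, yet the SAP gives it a worst-CTCAE-grade shift table with tested patients as the denominator

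*SAP*

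**What the plan says.** SAP section 4.2.1 (Laboratory assessments) states: "Shift tables for laboratory values by worst NCI CTCAE grade will be produced". The chemistry part of the list that follows begins "Clinical chemistry: ALT, AST, ALP, Total bilirubin, LDH, calcium, lipase, amylase" and carries no caveat for ALP.

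Protocol section 5.3.1, Table 3, defines the scheduled chemistry panel: "Serum creatinine, total bilirubin, aspartate transaminase (AST), alanine transaminase (ALT), thyroid stimulating hormone (TSH), blood urea nitrogen (BUN), lipase, amylase", followed by electrolytes and lactate dehydrogenase. ALP is not in it. ALP appears in a separate row headed "Additional laboratory tests (where clinically indicated only"), which also holds free T3 and free T4 and continues "creatinine clearance, alkaline phosphatase (ALP), autoimmune antibody test".

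On denominators, SAP section 3.1.2.3 says: "The denominator used in laboratory summaries of CTC grades will only include evaluable patients". For a grading criterion that does not use change from baseline, "to be evaluable the patient need only have 1 post dose-value recorded". SAP section 3.1.3 adds that missing safety data are generally not imputed, and its definition of baseline excludes unscheduled visits.

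For the two thyroid hormones in the same Table 3 row, SAP section 4.2.1 (Assessment of Thyrotoxicity) does something different and gives its reason: "Free T3 and free T4 will be listed only as they are to be tested only if clinically indicated".

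**The concern.** A test done on indication is done more often in patients in whom something is suspected. If the percentage is then taken among those tested, the group is enriched for abnormal results. The ALP row would sit beside ALT, AST and bilirubin, which are measured in everyone at every treatment visit, and nothing in the table would tell the reader that the two kinds of percentage are not comparable.

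There is a second problem, specific to a shift table. With no ALP scheduled at screening or Day 1, many patients with a post-dose value may have no baseline grade. For them there is no shift to report, and a rise that was present before treatment cannot be told apart from one that developed on it.

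The stake is modest but real. The study exists to describe safety, and SAP section 4.1 says its descriptive data may be used in support of health authority considerations.

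**Working it through.** **Step 1: is ALP the odd one out?** I compared the SAP shift list with Table 3. The haematology items (haemoglobin, leukocytes, lymphocytes, neutrophils, platelets) fall under the scheduled blood count with differential. Among the chemistry items, ALT, AST, total bilirubin, LDH, calcium, lipase, amylase, sodium, potassium, creatinine and urea nitrogen are all in the scheduled panel. ALP is the only analyte on the list that Table 3 reserves for clinical indication. The other tests in its Table 3 row (free T3, free T4, creatinine clearance, autoimmune antibodies) are not on the shift list.

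**Step 2: which denominator applies?** SAP section 4.1 sets percentages over the population total unless stated otherwise. Section 3.1.2.3 does state otherwise for CTC-grade summaries: evaluable patients only. So the ALP percentage is taken among those tested.

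**Step 3: direction and size.** The plan gives no figure to reproduce and no ALP testing frequency, so every input below is an assumption. Let p be the true share of patients with an abnormal worst grade, a the chance that an abnormal patient is tested, and b the chance that a normal patient is tested. Then

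share shown = p·a / (p·a + (1 − p)·b).

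For p = 10%:
- a = 80%, b = 40% (ratio 2): 0.08 / (0.08 + 0.36) = 18.2%
- a = 80%, b = 20% (ratio 4): 0.08 / (0.08 + 0.18) = 30.8%
- a = 90%, b = 10% (ratio 9): 0.09 / (0.09 + 0.09) = 50.0%

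Over a range of true rates, the share shown is:

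| Tested: abnormal / normal | Ratio | True 5% | True 10% | True 20% |
|---|---|---|---|---|
| equal | 1 | 5.0% | 10.0% | 20.0% |
| 80% / 40% | 2 | 9.5% | 18.2% | 33.3% |
| 80% / 20% | 4 | 17.4% | 30.8% | 50.0% |
| 90% / 10% | 9 | 32.1% | 50.0% | 69.2% |

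The share shown exceeds p whenever a > b, equals p when a = b, and falls below p when a < b.

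**Step 4: how many patients the row would rest on.** The share tested is p·a + (1 − p)·b. At p = 10% this is 44%, 26% and 18% in the three unequal cases. With the 600 to 1200 patients planned for Module A, that is 264 to 528, 156 to 312, and 108 to 216 patients.

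**Step 5: would the whole safety set be a better denominator?** No. The row would then show p·a, which at p = 10% is 8%, 8% or 9%. This is too low, because untested patients are counted as normal. Neither denominator recovers the true rate from tests done on indication.

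**The case against.** The strongest reply is that the direction is inferred. The documents do not define clinical indication for ALP or give a trigger for testing it, whereas free T3 and T4 have one (abnormal TSH or a suspected endocrine event). Indication could include monitoring of a known condition, and some sites may run ALP routinely. If testing is unrelated to ALP status there is no bias. Also, the overstatement applies to the worst-grade percentage. In the shift cells, missing baselines and patients already raised before treatment matter at least as much. All of this stands and limits the conclusion to likely overstatement of unknown size.

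Protocol section 4 allows the tumor-specific modules to add safety procedures. Neither Module A nor Appendix D on liver biochemistry was available to check, so scheduled ALP testing in Module A cannot be excluded.

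Three stronger readings are tempting and are not supported:
- A reader might infer that the SAP breaks its own general rule of listing such tests only. There is no such rule. The sentence concerns free T3 and T4; it is a precedent whose stated reason fits ALP equally well.
- A reader might infer that the trial will overstate hepatic toxicity. The SAP's liver section (threshold counts, potential Hy's law, narratives, plots) uses only ALT, AST and total bilirubin.
- A reader might put one striking figure on the gap. For example, if 15% were tested and half of those were raised, the table would show 50%, against 0.15 × 0.5 = 7.5% of all patients. Both inputs would be invented, and 7.5% is a floor because it treats every untested patient as normal.

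**Conclusion.** The point holds as a minor correction to one descriptive table. The testing rule in Table 3, the shift list and the evaluable-patient denominator do not fit together for ALP. Followed as written, the plan would report a percentage from a selected subset, often without a baseline grade, beside percentages from routinely measured analytes.

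This rests on two assumptions: that Module A does not schedule ALP, and that patients with abnormal ALP are more likely to be tested. Given both, the row overstates the rate by an amount the documents do not fix. At a true rate of 10% the illustrations run from no excess to a table value of 50%. No hypothesis is tested and no error rate is involved. The primary outcome is built on MedDRA groupings of AESI terms and does not depend on this table.

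**What to change.** First check whether Module A schedules ALP. If it does, a cross-reference in SAP section 4.2.1 settles the matter.

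If it does not, remove ALP from the clinical chemistry shift list and say that it is listed only, for the reason already given for free T3 and T4. No new listing is needed, because SAP section 4.1 already lists all data collected. Little safety information should be lost, since protocol section 6.3.7 has clinically relevant deteriorations in non-mandated parameters reported as adverse events.

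If the sponsor prefers to keep the row, it should show the number tested over the number in the safety set, carry a missing-baseline category, and have a footnote saying that testing was on clinical indication and that the percentage is not comparable with the other rows.

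The cost is one descriptive row lost or footnoted, and a one-line edit to the SAP.
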